## 8. Study Population

The study population will include mums, dads, and teachers who have contact with children ages 5 to 10 years old.

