## 9. Eligibility Criteria

Inclusion criteria

- be over the age of 18;
- be mums, dads or teachers likely to influence children 5-10 years old; and
- reside in either Australia, China, India, Indonesia, Saudi Arabia, South Africa, or the United Kingdom.

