## 11. Study Procedures

The survey were designed by consulting the literature and area experts and informed by a previous unregistered pilot survey. The items are designed to measure participants' demographics, hand-hygiene influencing, surface disinfecting, and self-reported confidence as described below.

*Design.*

- **Survey Section 1: Information/Consent Sheet. (1 item)**

Participants will be informed about the study and asked to give their informed consent before advancing. The information/consent sheet can be viewed in Appendix B.

- **Survey Section 2: Demographic items. (5 items)**

We will ask about participants' individual differences, age and gender.

Dem-Q1: How many years old are you?

Response Option

[drop down box if possible]

- 17 or fewer years old
- 18 – 30 years old
- 31 – 40 years old
- 40 – 50 years old
- 50 – 60 years old
- 61 – 70 years old
- 70 or more years old

An age-related demographic is necessary to confirm participants are of an acceptable age to take part in the survey, i.e. 18 or older.

If a person says '17 or fewer', they will not continue in the survey.

Dem-Q2: Are you employed as a full-time teacher for children from 5 to 10 years old?

Response Option

- Yes
- No

A teacher-employment item is necessary to ensure we include the planned number of teachers in the final survey (see Table 2 on p. 10).

Dem-Q3: Do you identify as a mum or dad of any children from 5 to 10 years old?

Response Option

- No
- Yes, a mum
- Yes, a dad

This parent item is necessary to ensure we include the planned number of mums and dads in the final survey. (see Table 2 on p. 10).

If a person says 'NO' and did not identify as a teacher in Q2, then they will not continue in the survey

Dem-Q4: With which gender do you identify?

Response Option

- Female
- Male
- Other/Prefer not to say

This is a regularly collected demographic, that we collect here because we cannot and will not use Q3 to infer participants genders. Further gender options, e.g. 'binary', are not included because these options do not translate well to all surveyed countries.

[If not teacher] Dem-Q5: Which one of the following best describes you?

Response Option

- Work full-time
- Work part-time
- Retired
- Full-time Home-maker / parent
- Student
- Unemployed
- Other

The work-related item is desirable attribute to better understand the participants in the survey participants in the survey.

- **Survey Section 3: Hand-hygiene influencing.**

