Appendix A. Survey items (finalized 09-Apr-2020)

Domain	Question Number	Handwashing Surface Disinfection	Parents	Teachers
Knowledge An awareness of the existence of something	1	H	I know that my children should wash their hands with soap and water for at least 20 seconds.	I know that my pupils should wash their hands with soap and water for at least 20 seconds.
	2	H	(RS) I do not know when my children should wash their hands with soap and water.	(RS) I do not know when my pupils should wash their hands with soap and water.
	3	H	(RS) I know that when my children's hands look clean, they are germ free.	(RS) I know that when my pupils hands look clean, they are germ free.
	4	SD	(RS) I know that when surfaces look clean, there are no germs.	(RS) I know that when surfaces look clean, there are no germs.
	5	SD	I know which surfaces I should disinfect in the home.	I know which surfaces I should disinfect in the classroom
Skills An ability or proficiency acquired through practice	6	H	I am able to teach my children to wash their hands.	I am able to teach my pupils to wash their hands.
	7	H	I am able to help my children develop good handwashing habits.	I am able to help my pupils develop good handwashing habits.
	8	H	(RS) I am not able to teach my children to wash their hands.	(RS) I am not able to teach my pupils to wash their hands.
	9	SD	I have the ability to disinfect surfaces in the home.	I have the ability to disinfect surfaces in the classroom
	10	SD	(RS) I do not have the ability to disinfect some of the surfaces in the home.	(RS) I do not have the ability to disinfect some of the surfaces in the classroom
Memory, attention and decision processes The ability to retain information, focus selectively on aspects of the environment and choose between two or more alternatives	11	H	I remind my children to wash their hands before eating.	I remind my pupils to wash their hands before eating.
	12	H	(RS) I forget to remind my children to wash their hands.	(RS) I forget to remind my pupils to wash their hands.
	13	H	(RS) There are many distractions that cause me to forget to remind my children to wash their hands.	(RS) There are many distractions that cause me to forget to remind my pupils to wash their hands.
	14	SD	I remember to disinfect the surface areas in my home every day.	I remember to disinfect the surface areas in the classroom every day.

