	27	H	(RS) I do not believe I can control whether my children wash their hands.	(RS) I do not believe I can control whether my pupils wash their hands.
	28	H	I believe that I can tell my children to wash their hands with soap and water.	I believe that I can tell my pupils to wash their hands with soap and water.
	29	SD	I believe that I am capable of disinfecting surfaces in my home.	I believe that I am capable of disinfecting surfaces in the classroom .
	30	SD	(RS) I believe that there is little I can do to disinfect surfaces in my home.	(RS) I believe that there is little I can do to disinfect surfaces in the classroom
Beliefs about consequences/ Optimism / Reinforcement (Belief) Acceptance of the truth, reality, or validity about outcomes of a behaviour in a given situation (Optimism) The confidence that things will happen for the best or that desired goals will be attained (Reinforcement) Increasing the probability of a response by arranging a dependent relationship, or contingency, between the response and a given stimulus	31	H	I believe that telling my children to wash their hands with soap and water will protect them from falling ill.	I believe that telling my pupils to wash their hands with soap and water will protect them from falling ill.
	32	H	(RS) I believe that children's handwashing habits have little effect on whether they get ill.	(RS) I believe that pupil's handwashing habits have little effect on whether they get ill.
	33	H	(RS) I believe that teaching my children to wash their hands is not worthwhile.	(RS) I believe that teaching my pupils to wash their hands is not worthwhile.
	34	SD	I believe that if I disinfect my home, my children will all fall ill less often.	I believe that if I disinfect the classroom my pupils will all fall ill less often.
	35	SD	(RS) I believe that disinfecting my home has no effect on how often my children get ill.	(RS) I believe that disinfecting my classroom has no effect on how often my pupils get ill.
	36	H	I intend to keep reminding my children to wash their hands before eating.	I intend to keep reminding my pupils to wash their hands before eating.

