	48	SD	I have the materials in my home to disinfect surfaces in my home.	I have the materials at my school to disinfect surfaces in the classroom .
Social influences (Those interpersonal processes that can cause individuals to change their thoughts, feelings, or behaviours)	49	H	People around me (such as my partner, family and friends) remind children to wash their hands.	My colleagues remind pupils to wash their hands.
	50	H	Most people in my culture practice good handwashing habits.	Most people in my culture practice good handwashing habits.
	51	H	(RS) It doesn't matter how clean my children's hands are if other people's children are not.	(RS) It doesn't matter how clean my pupil's hands are if other children's are not.
	52	SD	People around me (such as my partner, family and friends) encourage me to disinfect my home.	My colleagues encourage me to disinfect the classroom .
	53	SD	(RS) Few people around me (such as my partner, family and friends) disinfect surfaces in their homes.	(RS) Few of my colleagues disinfect surfaces in the classroom .
Self Confidence Questions		Self confidence	When your [children/pupils] can see you watching them, what percentage of the time do they wash their hands with soap and water after going to the toilet and before eating? [response options 0 - 100%]	When your [children/pupils] can see you watching them, what percentage of the time do they wash their hands with soap and water after going to the toilet and before eating? [response options 0 - 100%]
		Self confidence	When your [children/pupils] cannot see you watching them, what percentage of the time do they wash their hands with soap and water after going to the toilet and before eating? [response options 0 - 100%]	When your [children/pupils] cannot see you watching them, what percentage of the time do they wash their hands with soap and water after going to the toilet and before eating? [response options 0 - 100%]
		Self-confidence	What percentage of the time do you wash your own hands with soap and water after going to the toilet and before eating? [response options 0-100%]	

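### The survey selects parents through a child aged 5 to 10, but no item in Appendix A states that age range, so parents who also have younger or older children may give a blended answer that cannot be identified later

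*Combined protocol and SAP*

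**What the plan says.** Section 8 sets the target: "The study population will include mums, dads, and teachers who have contact with children ages 5 to 10 years old". Section 9 repeats it as an inclusion criterion: "be mums, dads or teachers likely to influence children 5-10 years old". Section 11 applies it to parents through Dem-Q3: "Do you identify as a mum or dad of any children from 5 to 10 years old". One child in the range is enough to qualify, whatever the ages of the others.

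After that screen the age range does not reappear. The typical parent item in Appendix A reads like item 11: "I remind my children to wash their hands before eating". The first confidence item asks: "When your [children/pupils] can see you watching them, what percentage of the time do they wash their hands with soap and water". The second has the same form for unobserved washing, and the third asks about the respondent's own hands.

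The five demographic items in Section 11 cover the respondent's age, teaching status, status as mum or dad, gender and work. None records how many children a parent has or how old they are.

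**The concern.** The group that qualifies a parent and the group the parent is asked about are not the same. Read literally, a parent of a 6-year-old and a 2-year-old, or of a 10-year-old and a 16-year-old, is asked for one answer covering both. Reminding a child, checking after the toilet and the share of unobserved occasions on which a child washes all plausibly depend on the child's age.

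The hand-hygiene items are the primary outcome (Section 10a) and feed the factor analysis. The confidence items are averaged into the regression outcome (Section 12b). If some parents blend in children outside the target range, these measures describe an unknown mix of ages, while the results are meant to inform a school-based intervention. Because children's ages are not recorded and the survey is anonymous, the affected parents cannot be singled out for adjustment or a sensitivity analysis.

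**Working it through.** The plan gives no figure on this point, so there is nothing to reproduce. The check is a count of item wording, followed by an illustration of size.

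**Item count, parent column of Appendix A**

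| Items | Total | Refer to the respondent's own children | State an age |
|---|---|---|---|
| Hand-hygiene | 33 | 30 | 0 |
| Surface disinfecting | 20 | 2 (items 34, 35) | 0 |
| All domain items | 53 | 32 | 0 |
| Confidence | 3 | 2 | 0 |

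The three hand-hygiene exceptions are:
- item 32, about children in general: "I believe that children's handwashing habits have little effect on whether they get ill";
- item 49, which asks whether people around the respondent "remind children to wash their hands";
- item 50, which does not mention children.

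**Instructions.** The descriptions of Survey Sections 3 and 5 in Section 11 cover random item order, the response scale, reverse scoring and the content of the confidence items. They contain no instruction about which children to consider.

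**Share of the sample concerned (Table 2)**
- Parents: India 375 + 375 = 750; six other countries 6 × (225 + 225) = 2,700; together 3,450.
- Teachers: 7 × 75 = 525.
- Total: 3,450 + 525 = 3,975. Parents are 3,450 / 3,975 = 87%.

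**Illustrative size.** All three inputs are assumptions; the documents give none of them.
- Share of parents with a child outside 5 to 10: 30% to 60%.
- Weight of that child in the answer: one half.
- Difference in washing between that child and the 5-to-10-year-old: 10 to 20 percentage points, always in the same direction.

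Shift in the parent mean of one child percentage item = share × weight × difference:
- low: 0.3 × 0.5 × 10 = 1.5 points;
- high: 0.6 × 0.5 × 20 = 6.0 points.

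The regression outcome averages the confidence items, of which two in three concern children:
- low: (2/3) × 1.5 = 1.0 point;
- high: (2/3) × 6.0 = 4.0 points.

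If younger siblings pull answers one way and older siblings the other, the net shift in the mean is smaller, although each blended answer remains ambiguous.

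**The case against.** The strongest reply is that the documents do not show that any blending occurs. Dem-Q3 names the age range shortly before the items, so respondents do receive a cue. Appendix B, the information sheet shown on the first screen, was not available for review and may frame the questions. Appendix A is a list of items rather than the on-screen questionnaire, so it may omit lead-in text. All of this stands, and it makes blending a risk and not a finding. It does not change the item wording, which is visible and carries no age. Dem-Q3 is an eligibility question, not an answering instruction.

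The reply can add that the aim and objectives (Sections 3 and 4) speak of children's hand-hygiene without an age, so choosing respondents by a child's age and then asking about their children generally could be deliberate. That is possible, but the plan does not say so, and Sections 8 and 9 define the population and eligibility by the age range.

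Four stronger readings are tempting and are not supported:
- **Every parent item is affected.** The counts above show otherwise. Role and resource items (for example 21-23 and 45-46) are also likely to depend little on a child's age.
- **Teachers are affected in the same way.** Dem-Q2 asks about full-time employment teaching children aged 5 to 10, so their pupils should largely be in range.
- **Country and age-group comparisons are biased.** That follows only if family composition differs between the groups, on which the documents give nothing. These comparisons are in any case exploratory.
- **The factor analysis is compromised.** A shift in item means does not by itself alter covariances. A varying mix of child ages could add shared variation across items and the outcome, but nothing here shows how much.

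**Conclusion.** The mismatch between the target age range and the item wording is documented and, with the planned data, cannot be corrected after collection. The most exposed items are those on reminding (11-13), those on checking (16-18) and the two child-washing percentages. The confidence outcome is affected through two of its three items.

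The size is unknown. The shifts of 1.5 to 6 points per child item and 1 to 4 points on the three-item average are illustrations that depend wholly on the assumed share, weight and one-directional difference. They should not be read as estimates of bias in this study. The point merits action because the remedy is cheap before launch and not available afterwards.

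**What to change.** Add a lead-in to Survey Sections 3 and 5: *Please answer only about your child or children (pupils) aged 5 to 10 years.* In the first two percentage items, write *your [children/pupils] aged 5 to 10*. In Survey Section 5 the lead-in should be placed so that it plainly does not govern the third item, which is about the respondent's own hands. The new text goes through translation and back-translation under Table 1.

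The cost is one sentence and two stems to translate, slightly longer text, and a small departure from the items finalized on 09-Apr-2020. No items or participants are added. If the information sheet or the on-screen survey already carries such an instruction, it is enough to reproduce it in the protocol. If the items can no longer change, the report should state that parents' answers may cover children outside 5 to 10 and that the extent cannot be determined.
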